Drs. [name], [name], [name] and/or research team members will continually assess the appropriate stimulation parameters including configurations, voltage and frequency. Stimulation parameters used during mapping, assessments and interventions will be closely monitored by the research team. Every research participant will be slowly acclimated to stimulation. This may help them avoid experiencing significant blood pressure fluctuations or dizziness. However, if these conditions should occur, stimulation will be modified or stopped, depending on the need to regulate the blood pressure. Blood pressure and heart rate will be closely monitored throughout stimulation sessions in the lab. Stimulation will immediately cease if these values become abnormal or if the research participant feels tired, winded or has chest pain. If these conditions persist, the stimulation will be immediately discontinued and the research nurse will be contacted immediately to assess the research participant. If needed the study physician or physician assistant will be notified and will also examine the individual. Immediate medical care will be provided when necessary. Their primary care provider will be informed when necessary.

Research participants will undergo training about stimulator use for each configuration and intervention. Testing of optimal stimulation parameters and ranges will be performed in the laboratory to make sure stimulation is safe for the research participant. Stimulation programs given to each participant will be restricted to those used and tested in the laboratory. Participants will be instructed to call the research physical therapist and/or assigned research team member immediately if complication from stimulation develops during home training programs. If serious adverse effects such as autonomic dysreflexia, sustained elevation or reduction in blood pressure or bradycardia or tachycardia have recurring onset on an individual or become present across the tested sample population the research team will evaluate the stimulation protocol. Stimulation parameters will be assessed initially limiting the voltage and frequency as well as selecting more localized configuration patterns that could reduce such effects. If a serious adverse event occurs as a result of stimulation, the

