A medical event is defined within our program as “any untoward or unfavorable medical occurrence in a human research participant that occurs during the same time period the research participant is enrolled in the study and is not study related and is not serious.” It is an anticipated medical issue that is unfortunately common to individuals with chronic spinal cord injury and can occur daily, weekly monthly, or several times a year. These medical events can include urinary tract infections, kidney stones, hypotension, autonomic dysreflexia, skin sores and pressure sores with prolonged healing, joint swelling, joint soreness, joint sprain, ligament sprain, fracture, infections (non-UTI), spasticity and falls. Our standard operating procedure is that if any of these medical issues arise while directly participating in our research, if not immediately resolved, the study physician is notified and the individual is referred to the appropriate medical care. This medical care can be provided by our study physician or their colleagues or by the medical specialist of the research participant’s choice. The study physician can medically treat the issue to resolution, if appropriate, and the research participant chooses the study physician as their clinical choice for medical treatment. In this case the study physician would notify the principal investigator only if the medical issue affects their medical eligibility in the study or any of the research assessments or training paradigms. If another physician treats the medical issue the study physician will follow the individual to only assess whether the medical condition affects their medical eligibility in the study or any of the research assessments or training paradigms and will notify the principal investigator. All non-study related medical events are followed by the research team and will be reported to the IRB at the time of the continuing annual review. A weekly report of all medical events is generated by the research nurse and sent to the study physician (and physician assistant), the principal investigator, and the study physical therapists.

E. Data and Safety Monitoring Board

[name], PhD (Chair of DSMB)

Neurosurgeon, Clinical Professor

Department of Neurological Surgery

University of Miami and The Miami Project to Cure Paralysis, Miami, FL

[name]

Cardiologist, Professor of Medicine

Johns Hopkins Hospital, Baltimore, MD

[name], PhD

Urologist

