University of Zurich Spinal Cord Injury Center, Research

Balgrist University Hospital, Zurich, Switzerland

[name]
Medical Director, Spinal Cord Injury Rehabilitation
Kessler Institute for Rehabilitation, West Orange, NJ

An independent Data Safety Monitoring Board (DSMB) has been chartered to monitor the safety of research participants as well as the validity and integrity of studies conducted at the Kentucky Spinal Cord Injury Research Center, University of Louisville and the Frazier Rehab Institute. Members of the DSMB serve in an individual capacity and will convene yearly to provide their expertise including recommendations regarding the continuation, modification, or termination of any or all phases of a study. The first DSMB meeting will occur in the first quarter of the first year of the funding period and will then meet yearly after that. The DSMB will review cumulative study data to evaluate safety, study conduct, scientific validity and data integrity. DSMB members may review current versions of the protocol and Informed Consent Form, and any subsequent amendments to ensure an understanding of a study's objectives and design. Day-to-day oversight of the study will be provided by the Principal Investigators. They will review all study data and any adverse events, and report all adverse events to the IRB and DSMB chairperson as appropriate. Medical events that occur while the research participants are engaged in the research protocols also will be logged by a research nurse, research physical therapists, study physicians and/or research staff. Any adverse events are collected on an Adverse Event Form and will be reported at the yearly DSMB meeting. An Adverse Event report will be generated for each event and will include a description of the event, when and how it was reported, as well as any official chart records or documentation to corroborate the event and a determination of attribution. Any Adverse Event that the principal investigator determines to be definitely, probably, or possibly related to the research intervention, or serious in nature, and unexpected will be reported to the IRB within 5 business days of the principal investigator gaining knowledge of the event. Any unanticipated problems involving risks to research participants or others will include a corrective plan and measures to prevent reoccurrence. Such events will be reported to appropriate regulatory agencies as required within 5 business days of the principal investigator gaining knowledge of the event.

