Appendix #2

Medical Event Reporting Unrelated to the Research Protocol Version 2, 12/12/2016

A medical event is defined within our program as any untoward or unfavorable medical occurrence in a human research participant that occurs during the enrollment period of a study.

As the team is made aware of study participants' medical events, they will be recorded in a log for tracking and reporting.

Medical events that occur during a research visit will be reported to the study nurse and then elevated to the study physician if not immediately resolved. The physician will evaluate these medical events, to determine causality with relation to the research and referral for medical care.

A weekly report of all medical events is generated by the research nurse and sent to the study physician (and physician assistant), the principal investigator, the regulatory core, and the study therapists for review of causality and follow-up.

We have developed a table outlining the most common expected events in the spinal cord injury (SCI) population. These events occur with this population on a frequent basis. This table will allow the IRB and our staff to understand how expected and unrelated events will be documented and reported.

If a physician outside the study team treats the medical event, the study physician will follow the event to assess the following:

- The medical condition affecting their medical eligibility for research
- Determination on causality of the event
- The event's effect on research assessments and/or training paradigms

All conclusions reached by the study physician will be reported to the PI.

Characteristics of Medical Events in the Spinal Cord Injury Population (Unrelated to Study)					
Medical Event	Probability	Medical Event Severity	Medical Intervention	Serious Event	Reporting
Urinary Tract Infections	Likely	Mild	Antibiotics	No	Research Medical Log
	Likely	Moderate	Antibiotics	No	Research Medical Log
	Rare	Moderate	Hospitalization	No	IRB Continuation Review
	Rare	Severe	Hospitalization	Yes	IRB Continuation Review
Urinary Tract Infections that significantly interfere with research conduct	Rare	Moderate	Depends on specific diagnosis	No	IRB Continuation Review
	Rare	Moderate	Hospitalization	No	IRB Continuation Review
	Rare	Moderate	Hospitalization	Yes	IRB Continuation Review
Urinary Tract Infection/Kidney	Less Likely	Moderate	Depends on specific diagnosis	No	Research Medical Log
	Rare	Moderate	Hospitalization	No	IRB Continuation Review

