	Rare	Severe	Hospitalization	Yes	IRB Continuation Review
Urinary Tract Infections/Kidney that significantly interfere with research conduct	Rare	Moderate	Depends on specific diagnosis	No	IRB Continuation Review
	Rare	Moderate	Hospitalization	No	IRB Continuation Review
	Rare	Severe	Hospitalization	Yes	IRB Continuation Review

Characteristics of Medical Events in the Spinal Cord Injury Population (Unrelated to Study)					
Medical Event	Probability	Medical Event Severity	Medical Intervention	Serious Event	Reporting
Kidney Stones	Less Likely	Moderate	Depends on specific diagnosis	No	Research Medical Log
	Rare	Moderate	Hospitalization	No	IRB Continuation Review
	Rare	Severe	Hospitalization	Yes	IRB Continuation Review
Kidney Stones – significantly interferes with research conduct	Rare	Moderate	Depends on specific diagnosis	No	IRB Continuation Review
	Rare	Moderate	Hospitalization	No	IRB Continuation Review
	Rare	Severe	Hospitalization	Yes	IRB Continuation Review

Characteristics of Medical Events in the Spinal Cord Injury Population (Unrelated to Study)					
Medical Event	Probability	Medical Event Severity	Medical Intervention	Serious Event	Reporting
Hypotension	Likely	Mild	None	No	None
	Rare	Moderate	Physician Referral	No	Research Medical Log
	Rare	Moderate	Depends on specific diagnosis; includes medication and/or hospitalization	No	IRB Continuation Review
	Rare	Severe	Depends on specific diagnosis; includes medication and/or hospitalization	Yes	IRB Continuation Review
Hypotension that interferes with research conduct	Less Likely	Moderate	Cease stand or step; Elevate legs above heart	No	None
	Rare	Moderate	Physician Referral	No	Research Medical Log
Hypotension that significantly interferes with research conduct	Rare	Moderate	Depends on specific diagnosis; includes medication and/or hospitalization	No	IRB Continuation Review
	Rare	Severe	Depends on specific diagnosis; includes medication and/or hospitalization	Yes	IRB Continuation Review

Characteristics of Medical Events in the Spinal Cord Injury Population (Unrelated to Study)					
Medical Event	Probability	Medical Event Severity	Medical Intervention	Serious Event	Reporting
Autonomic Dysreflexia	Likely	Mild	None	No	None
	Less Likely	Moderate	Identify and eliminate source	No	None
	Rare	Moderate	Depends on specific diagnosis; includes medication and/or hospitalization	No	IRB Continuation Review
	Rare	Severe	Depends on specific diagnosis; includes medication and/or hospitalization	Yes	IRB Continuation Review

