Autonomic Dysreflexia that significantly interferes with research conduct	Rare	Moderate	Physician Referral	No	IRB Continuation Review
	Rare	Moderate	Depends on specific diagnosis; includes medication and/or hospitalization	No	IRB Continuation Review
	Rare	Severe	Depends on specific diagnosis; includes medication and/or hospitalization	Yes	IRB Continuation Review

Characteristics of Medical Events in the Spinal Cord Injury Population (Unrelated to Study)					
Medical Event	Probability	Medical Event Severity	Medical Intervention	Serious Event	Reporting
Skin sore	Likely	Mild	None	No	None
Skin sore that requires prolonged healing	Likely	Mild	None	No	None
	Likely	Moderate	None	No	Research Medical Log
	Less Likely	Moderate	Wound Care referral	No	Research Medical Log
	Rare	Moderate	Hospitalization	No	IRB Continuation Review
	Rare	Severe	Hospitalization	Yes	IRB Continuation Review
Skin sore that requires prolonged healing and that interferes with research conduct	Rare	Moderate	Depends on specific diagnosis	No	IRB Continuation Review
	Rare	Severe	Depends on specific diagnosis	Yes	IRB Continuation Review
Skin sore that requires prolonged healing and results in infection	Less Likely	Mild	Depends on specific diagnosis	No	Research Medical Log
	Less Likely	Moderate	Depends on specific Diagnosis	No	Research Medical Log
	Rare	Moderate	Hospitalization	No	IRB Continuation Review
	Rare	Severe	Hospitalization	Yes	IRB Continuation Review
Skin sore that requires prolonged healing and results in infection and interferes with research conduct	Rare	Moderate	Depends on specific diagnosis	No	IRB Continuation Review
	Rare	Severe	Depends on specific diagnosis	Yes	IRB Continuation Review

Characteristics of Medical Events in the Spinal Cord Injury Population (Unrelated to Study)					
Medical Event	Probability	Medical Event Severity	Medical Intervention	Serious Event	Reporting
Joint soreness with swelling	Likely	Mild	None	No	None
	Less Likely	Moderate - Reoccurs	None	No	Research Medical Log
	Less Likely	Moderate - Reoccurs	Physician referral for X-ray	No	Research Medical Log
Joint soreness with swelling that interferes with research conduct	Less Likely	Moderate - Reoccurs	Depends on diagnosis	No	IRB Continuation Review
Joint soreness with swelling – fracture or other orthopedic injury	Less Likely	Moderate	Depends on diagnosis	No	IRB Continuation Review
	Rare	Serious	Depends on Diagnosis	Yes	IRB Continuation Review

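### Appendix #2 gives a reporting entry of *None* to session-stopping hypotension and to moderate dysreflexia needing its source removed, contradicting the protocol's own logging and review rules

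*Protocol*

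**What the plan says.** The Appendix #2 table is headed "Characteristics of Medical Events in the Spinal Cord Injury Population (Unrelated to Study", and the text before it says that it shows how expected, unrelated events are documented as well as reported. Its Reporting column takes three values: *None*, *Research Medical Log* and *IRB Continuation Review*.

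Two rows matter here. Both are classed Less Likely, Moderate and not serious, and both have Reporting *None*:
- Hypotension that interferes with research conduct, with the intervention "Cease stand or step; Elevate legs above heart".
- Autonomic dysreflexia, with the intervention "Identify and eliminate source".

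The surrounding text says something different:
- **Appendix #2, text.** When the team learns of medical events, "they will be recorded in a log for tracking and reporting". The research nurse compiles a weekly report covering every medical event, which goes to the study physician, the principal investigator and others for causality review. An event during a research visit goes to the nurse first, and to the physician only if it does not resolve immediately.
- **Section IV.E.** "Medical events that occur while the research participants are engaged in the research protocols also will be logged". Adverse events, collected on their own form, go to the yearly DSMB meeting.
- **Section IV.D.** All medical events unrelated to the study are reported to the IRB at annual review. A medical event is defined there as one that "is not study related and is not serious".
- **Section IV.B.** Dysreflexia that resolves once its cause is removed is a Likely risk of the bladder and bowel assessments. Significant heart-rate or blood-pressure change is a Likely risk of those assessments and a Less Likely risk of the stand, voluntary and cardiovascular training.

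**The concern.** *Research Medical Log* is itself a value in the Reporting column, and the table is said to govern documentation. A member of staff would therefore naturally read *None* as meaning not even a log entry. That instruction cannot be followed together with the text of Appendix #2, Section IV.D and Section IV.E.

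The rows affected are not trivial ones. The stimulation is intended to change blood pressure, and stand training is always given with stimulation (Section III.E.4). Hypotension that stops a stand is therefore an event whose relation to the intervention needs to be judged. It should not be settled by a table heading. What is at stake is the completeness of the safety record for this kind of event. In the first period only Group B receives stand training, so any under-recording of hypotension during stand training would fall on that group.

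**Working it through.** The plan gives no figure to reproduce. The check is a count of table rows and a comparison of the places that govern the same event.

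**1. Rows with Reporting *None* in Appendix #2.**

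| Event | Rows marked *None* | Of these, with an intervention |
|---|---|---|
| Hypotension | 1 | 0 |
| Hypotension that interferes | 1 | 1 |
| Autonomic dysreflexia | 2 (mild; moderate) | 1 (moderate) |
| Skin sore | 1 | 0 |
| Skin sore, prolonged healing | 1 | 0 |
| Joint soreness with swelling | 1 | 0 |
| Infections (non-UTI) | 1 | 0 |
| Falls | 1 | 0 |
| Spasticity | 2 (mild; moderate) | 0 |
| **Total** | **11** | **2** |

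The two rows with an intervention are the two at issue.

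**2. Rows labelled as interfering, or significantly interfering, with research conduct.** UTI 3, UTI/kidney 3, kidney stones 3, hypotension 2 + 2, dysreflexia 3, skin sore 2 + 2, joint soreness 1 + 2, infections 3, falls 3, spasticity 3. The sum is 32. Thirty go to *IRB Continuation Review*, one goes to the log (hypotension with physician referral) and one is *None* (hypotension that stops a stand or step).

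**3. The two event blocks.**
- Hypotension, 8 rows: 2 *None*, 2 *Research Medical Log*, 4 *IRB Continuation Review*.
- Dysreflexia, 7 rows: 2 *None*, 5 *IRB Continuation Review*. All three rows under "Autonomic Dysreflexia that significantly interferes with research conduct" go to the IRB.
- No row in either block names the DSMB.

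**4. Comparison with other moderate rows.** A moderate fall, a moderate non-UTI infection, moderate recurrent joint soreness and a moderate slow-healing skin sore, each with no medical intervention, all go to the log. Moderate spasticity with no intervention does not. The table is thus mostly stricter for moderate events needing nothing than for the two needing action.

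**5. The same episode under each rule.** Take hypotension during stand training that resolves when the legs are raised.

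| Source | What happens to it |
|---|---|
| Appendix #2 table | *None* |
| Appendix #2 text | Logged, in the weekly report, reviewed for causality; need not reach the physician at the time |
| Section IV.E | Logged, because it occurred during research |
| Section IV.D | Reported to the IRB at annual review if unrelated |
| Section IV.B | Blood-pressure change is a listed risk of the training |

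The first line cannot be reconciled with the next three. If the table is followed, the episode has no log entry from which the weekly report could pick it up, and immediate resolution removes the one other stated path to the physician.

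**6. Definition.** Section IV.D confines medical events to non-serious ones. The Appendix #2 definition drops that limit, and the table contains rows marked serious. In the hypotension and dysreflexia blocks there are 2 + 2 = 4 such rows, all sent to *IRB Continuation Review*.

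**The case against.** The strongest reply is that the text already provides what is needed. It requires a log, a weekly report to the people who judge causality and an annual IRB report, and nothing says that the table overrides it. Section IV.C.2.a also has a team member sign when a session passes without a medical event, so a session with an event would lack that signature. Events judged possibly related would be adverse events under Section IV.E and would reach the DSMB on that form. This stands as far as it goes: the record exists if staff follow the text. It does not remove the contradiction, because the table is the document staff would consult for a given event.

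Stronger readings are tempting, and the documents do not support them:
- **That no data on these events would exist.** The text requires logging and weekly review, and the DSMB has a general remit over cumulative study data.
- **That the recurrence rule is disabled.** Section IV.C.2.b acts when effects "have recurring onset on an individual or become present across the tested sample population the research team will evaluate the stimulation protocol", but that sentence concerns serious adverse effects. The two rows are classed not serious, so they are not clearly inputs to it.
- **That dysreflexia interrupting a session goes unreported.** Every dysreflexia row that names significant interference goes to the IRB. The *None* rows are mild dysreflexia, or moderate dysreflexia resolved by removing the source, and neither mentions interruption.
- **That about 4 to 11 of 36 participants would be affected** (36 × 0.11 = 4.0; 36 × 0.30 = 10.8). This borrows the 11–30% class from Section IV.B, which grades study risks. Appendix #2 describes events in the SCI population and gives neither percentages nor a per-participant basis.
- **That sending serious rows to continuing review breaches the five-day rule.** As Section IV.E is worded, that rule can be read as applying only to unexpected events, and the table lists expected ones. The mismatch in definition remains.

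**Conclusion.** The contradiction is real and narrow. Two *None* entries conflict with three statements elsewhere in the protocol, for kinds of event that the protocol itself lists as risks of its procedures. One of the two, session-stopping hypotension, is the single exception among 32 interference rows. The consequence is conditional: if staff follow the table, in-session episodes that resolve at once could go unlogged and miss causality review. Separately, and whichever text prevails, an event classed as an unrelated medical event has no express route to the DSMB. The conclusion rests on reading *None* as distinct from *Research Medical Log*, which the column's own values and the table's stated purpose support. The number of events cannot be estimated from the documents. The point should be corrected, since it concerns safety data and costs almost nothing to put right.

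**What to change.** Three edits, all to record-keeping and none to clinical management:
1. In Appendix #2, replace *None* with *Research Medical Log* for hypotension or dysreflexia arising during stimulation, an assessment or a training session.
2. State that the unrelated table applies only after the causality review described in the Appendix #2 text, including for events that resolved at once.
3. Reconcile the non-serious definition in Section IV.D with the Appendix #2 definition and the rows marked serious, and check that the reporting routes in Sections IV.D, IV.E and Appendix #2 then agree. The same edit should say whether, and how, unrelated medical events reach the DSMB.

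The cost is the table and text edits and some additional log entries. The research nurse already produces the weekly report that would carry them.
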